# 8. Biometrics

## 8.1 Data Management The data

collected for the studies (patient and disease-related data, imaging and laboratory data, radiation treatment planning parameters) are recorded and processed electronically (eCRFs – REDCap). In the event of withdrawal from the study, the data already collected may be used for analysis unless an explicit revocation of consent has been received.

All patient data is collected pseudonymously. Each patient is assigned an individual identification number, and only the participating personnel at the study center have access.

The list containing the mapping of full names to identification numbers is stored. This list is treated with strict confidentiality and retained for 10 years after the study's completion. All data entered into the database is pseudonymized. The completed PSMA-PET/CT scans and radiation treatment plans are also sent pseudonymized to the study center in Tübingen.

The principal investigators at each site are obligated to ensure compliance with legal and radiation protection regulations during the study and to uphold the principles of good scientific and clinical practice. Furthermore, they must ensure the correct and complete entry of data into the eCRFs.

The data collected as part of the study must be entered into the eCRFs by authorized and designated personnel. Authorization for this is granted after appropriate training and a written agreement and designation in the Delegation Log. Only trained, registered, and authorized personnel will have access to the eCRF database.

The data in the RED-Cap database are subjected to queries so that the persons responsible for the database at the study center (study nurse or study physician) can check the entries for discrepancies and correct them if necessary.

## 8.2 Evaluation Populations

Statistical analysis is planned according to intent-to-treat (ITT) and per-protocol (PP) data. **The intent-to-treat population** comprises all patients enrolled in the study who received at least one treatment and for whom some data (baseline questionnaires) are available. The **per-protocol population** comprises all patients in whom the planned therapy was fully completed according to the study protocol and for whom all relevant data are complete and documented.

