## 4. Description of the clinical study

### 4.1 Study design and rationale

This study is a non-randomized, single-stage phase II trial with a Fleming design. No control group is included because both ablative radiotherapy of metastases and (ultra-)hypofractionated radiotherapy of the prostate are standard treatment in curative and limited metastatic disease settings and have been validated in independent studies [11, 12, 24].

Several studies have demonstrated the benefit of MDT even in cases of polymetastatic disease, with a well-tolerated side effect profile [15, 16, 23, 25]. In a single-center series where patients with bone metastases, with and without prior prostate therapy, received ablative MDT plus antiandrogen therapy, a 2-year progression-free survival (PFS) was achieved in 40% of patients. Three-quarters of patients who experienced recurrent bone metastases received MDT again, thus delaying the need to switch systemic therapy. No high-grade adverse events (CTCAE grade 3 or higher) were observed with MDT.

The ultrahypofractionated radiotherapy of the prostate in this study is planned analogously to the PACE-B trial. In that trial, non-metastatic patients received primary radiotherapy of the prostate with 36.25 Gy/40.0 Gy to the PTV/CTV in five fractions with a single dose of 7.25 Gy/8.0 Gy. The 5-year toxicity analysis showed no increase in side effects with ultrahypofractionation in primary radiotherapy of the prostate compared to the normofractionated standard of care with 78 Gy [26]. Furthermore, the present study omits the administration of a prostate boost, thus limiting the single dose to 7.25 Gy and the total dose to 36.25 Gy. As an alternative treatment regimen (in case of technical or medical contraindication to ultrahypofractionation, radiation therapy with moderate hypofractionation with 20 x 3 Gy single dose (analogous to the CHHiP trial [27]) or radiation therapy according to departmental standard, e.g. analogous to the STAMPEDE study with 6 x 6.0 Gy) is performed.

[figure not shown]
The STAMPEDE study, which investigated the effect of PDT in combination with standard-of-care therapy in patients with primary metastatic disease, demonstrated a benefit in overall survival from local therapy of the prostate in cases of limited metastasis [11].

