#### 4.4 Sample Size Estimation and Recruitment Period Based on existing

publications regarding PSA response to complete androgen blockade and irradiation of bone metastases, a radiological response after RECIP with a PSMA volume reduction of at least 30% is expected to be achieved in 40% of patients through the study intervention. If the success rate remains below 15%, it is assumed that the therapy provides no benefit. The study hypothesis will be rejected with a sample size of 27 patients (power of 90%, one-sided significance level  $\alpha=0.05$ ) if  $>5/27$  patients do not show a response after RECIP 12 months following metastasis-directed therapy.

At the urological center in Tübingen, approximately one patient per week with a new diagnosis of primary bone metastases in prostate cancer is presented to the tumor board. Considering the expected inadequate treatment response in approximately 20-30% of cases and adhering to the inclusion and exclusion criteria, a realistic number of 5-10 patients per center could be enrolled within one year. Therefore, a recruitment period of 12 months was chosen for the target of 6 centers.

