## 5.5 Patient discharge

Patients included in the study can withdraw from the study at any time at their own request and without giving reasons, and without affecting any future treatment or regular follow-up care after radiation therapy.

Exclusion from the study may occur at the discretion of the study physician for reasons of health risk (for example, if a serious comorbidity is present or if the planned radiation therapy is not possible due to prior radiation treatment). In the event of withdrawal from the study, the reason will be documented in the respective patient file and in the eCRF (CRF Drop-Out).

All patients who prematurely withdraw from the study after having already undergone a study intervention should receive a final examination immediately upon withdrawal, which should be documented in the eCRF (CRF Follow-Up). Furthermore, they should be offered a connection to the center as part of their regular radiotherapy follow-up care.

If consent to participate in the study is withdrawn, no further clinical data will be collected and no further study visits will be conducted. If a study intervention has already taken place, continued contact with the center for routine follow-up care after radiotherapy will be offered; no study data will be collected during this follow-up, only routine radiotherapy follow-up care will be provided. All data collected up to this point will be anonymized immediately, unless a request for complete data deletion is received. Treatment plans for treatments already administered within the study must be retained for 30 years in accordance with radiation protection regulations.

A cancellation of the planned study measures may become necessary for the following reasons:

- Disease progression necessitating the initiation of chemotherapy (e.g. Occurrence of visceral metastasis).
- Deterioration of general health, which precludes the continuation of the planned Measures prevented.
- An increase or doubling of the PSA level compared to baseline that is not attributable to a lesion requiring local therapy and necessitates a change in systemic therapy. If PSA progression according to Phoenix criteria is present, the next scheduled PSMA-PET scan is prioritized, and if isolated metastases are found, stereotactic radiotherapy is performed again. In cases of diffuse progression or the presence of visceral metastases, the therapy is adjusted according to the tumor board of the respective center.

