## 8.3 Statistical Analysis

All planned analyses will be performed for both the ITT and PP populations. A descriptive analysis of the primary and secondary endpoints will be conducted by determining relevant statistical parameters (including mean, median, standard deviation, minimum, maximum, absolute and relative frequencies, qualitative assessment of quality of life and side effects) and calculating the corresponding 95% confidence intervals. Furthermore, a descriptive analysis of the radiation treatment plans is planned. Endpoints collected at different time points (including side effects, quality of life, and PSA levels) will be described for each time point, and their temporal progression will be visualized graphically.

For endpoints that represent an interval until an event (progression-free survival, time to change of systemic therapy, overall survival), an evaluation is also performed using Kaplan-Meier curves and log-rank tests. In addition, a Cox regression analysis is conducted to investigate potential influencing factors on the respective analyzed endpoints.

If indicated by the patients, the reasons for premature discontinuation of therapy will be investigated. In addition, the reasons for withdrawal from the program documented by the center will be reviewed.

Study and loss-to-follow-up analyzed.

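### The primary endpoint is analysed in both ITT and per-protocol sets without saying which decides, and per-protocol exclusion depends partly on outcome, so its response rate can be biased upward

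*Protocol*

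**What the plan says.** Section 4.1 sets the design: "This study is a non-randomized, single-stage phase II trial with a Fleming design". Section 4.4 gives the null and target rates: "If the success rate remains below 15%, it is assumed that the therapy provides no benefit", and a response "is expected to be achieved in 40% of patients through the study intervention". The size is a "sample size of 27 patients (power of 90%, one-sided significance level" of 0.05). The decision rule there is written on a denominator of 27 only. No allowance for dropout or unevaluable scans is stated.

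Section 8.2 defines two sets. ITT contains enrolled patients "who received at least one treatment and for whom some data (baseline questionnaires) are available". PP contains "all patients in whom the planned therapy was fully completed according to the study protocol and for whom all relevant data are complete". Section 8.3 then states: "All planned analyses will be performed for both the ITT and PP populations". Neither set is named as primary.

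Other sections determine who can reach PP:
- Sections 4.2 and 4.3.2 place metastasis radiotherapy six months after prostate radiotherapy.
- Sections 4.3.1 and 7.3 place the response PET 18 months after prostate radiotherapy. Section 7.3 brings it forward on a PSA rise.
- Section 5.5 lists reasons why study measures may be cancelled. Among them are "Disease progression necessitating the initiation of chemotherapy", a PSA rise that requires a change of systemic therapy, and spread of active lesions beyond what local treatment can address.

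**The concern.** A patient whose measures are cancelled for progression before metastasis radiotherapy is finished has not completed the planned therapy, so he leaves PP. The same happens if stopping early leaves the response scan missing. Clinically these patients have failed. Removing them takes non-responders out of the denominator and leaves the numerator alone, and with no control arm nothing offsets the shift.

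Because no set is named as decisive, a PP result above the threshold could be reported as success when the all-patient result falls short. This matters beyond a pilot: section 2.4 says the combination will be routinely offered once the primary endpoint is reached, and the synopsis and section 3.3 make a follow-on trial depend on it.

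Two lesser points belong here. The ITT definition depends on baseline questionnaires, which have no bearing on a PET endpoint. And section 4.4 does not say whether its 40% refers to all 27 patients or only to those with an evaluable scan.

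**Working it through.** **Inputs.** From section 4.4: n = 27, null rate 0.15, target rate 0.40, one-sided alpha 0.05, power 90%. Assumed here because the protocol gives no figure: PP exclusion of 10% to 30%, and 1 to 5 unevaluable patients. For sets smaller than 27 the protocol gives no threshold, so I use the smallest c with P(X ≥ c | n, 0.15) ≤ 0.05.

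**1. The plan's own figure.** For n = 27 that cut-off is 8 responders:
- P(X ≥ 8 | 27, 0.15) = 0.0398
- P(X ≥ 8 | 27, 0.40) = 0.9047

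The stated 27 patients and 90% power are reproduced.

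**2. Can the two sets disagree?** Take 7 responders in all and exclude only non-responders from PP. The p-value is P(X ≥ 7 | n, 0.15).

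| PP size | Excluded | p | Passes 5%? |
|---|---|---|---|
| 27 | 0 | 0.099 | no |
| 26 | 1 | 0.083 | no |
| 25 | 2 | 0.070 | no |
| 24 | 3 | 0.057 | no |
| 23 | 4 | 0.046 | yes |
| 22 | 5 | 0.037 | yes |

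The verdict changes only from the fourth excluded non-responder, which is 4/27 = 15% of the patients. With one to three exclusions the cut-off remains 8, so the sets agree. Disagreement can also run the other way: 8/27 passes (p = 0.0398), but if one responder is dropped for incomplete data, 7/26 fails (p = 0.083).

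**3. PP type I error.** Let the true rate in all patients be 0.15, let each patient leave PP with probability d, and let everyone who leaves be a non-responder. The rate among those who stay is then 0.15/(1 − d), and the error is

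sum over k of P(K = k | 27, d) × P(X ≥ c(27 − k) | 27 − k, 0.15/(1 − d)).

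| d (assumed) | rate in PP | PP type I error |
|---|---|---|
| 10% | 0.167 | 0.052 |
| 15% | 0.176 | 0.069 |
| 20% | 0.188 | 0.087 |
| 30% | 0.214 | 0.133 |

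For all 27 patients with cut-off 8 it is 0.040 throughout.

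**4. What the 90% power assumes.** If 40% is the response rate in all 27, with unevaluable patients already counted as failures, power stays at 0.905. If 40% applies only to evaluable patients, and m unevaluable patients count as non-responders against a cut-off of 8, power is P(X ≥ 8 | 27 − m, 0.40):
- m = 1: 0.878
- m = 2: 0.846
- m = 3: 0.808
- m = 5: 0.710

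**The case against.** The best defence is that reporting ITT and PP side by side is ordinary practice, that any PP set leaves out non-completers, and that the naming of a primary set and the scoring of missing scans are often left to the SAP. The one decision rule in section 4.4 is written on 27, which hints at an all-patient denominator. Section 8.3 describes the analysis as descriptive with confidence intervals, so no PP test is actually specified.

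Part of this stands. The cut-offs below 27 and the exclusion rates are mine, and the error figures are conditional on them. At 10% exclusion the PP error is 5.2%, close to nominal. What does not go away is that the protocol itself defines both sets and applies them without rank to every analysis. Section 4.4 names no set, and even ITT as defined can fall below 27.

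Three stronger readings should be resisted:
- A reader might infer that PP removes all failures. It does not. A patient who completes both steps and does not respond stays in. Cancellation under 5.5 is possible, not automatic, and the scan brought forward under 7.3 will document some progressors.
- A reader might infer that the 90% power is wrong. It is not, if the 40% of patients in 4.4 already counts unevaluable patients as failures. The text does not say.
- A reader might infer that the questionnaire condition materially shrinks ITT. Baseline questionnaires are collected at enrolment, so few treated patients are likely to be lost. It is a minor point of wording.

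**Conclusion.** The point holds in a limited form. The protocol runs its primary analysis in two sets without saying which decides, and one of them excludes patients for reasons tied to outcome. The PP response rate can therefore be biased upward.

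Opposite verdicts are possible but not inevitable. When they arise only from dropping failures, they need at least four excluded non-responders among 27. The inflation of PP type I error ranges from negligible (about 5% at 10% exclusion) to substantial (about 13% at 30%). It rests on assumed exclusion rates, on all excluded patients being non-responders, and on an exact 5% cut-off for each set size. The power question is a missing statement of what the 40% refers to, not an error in the stated sample size. This should be corrected before the analysis, but it does not undermine the design.

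**What to change.** In 8.2 and 8.3, state that:
- the primary decision uses all patients who started study radiotherapy, with no questionnaire condition;
- a patient with no evaluable post-treatment response PET, whether at month 18 or brought forward under 7.3, counts as a non-responder, so a valid early scan is used and not treated as missing;
- PP is supportive only.

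Apply the section 4.4 threshold to that set once its wording is corrected. The present phrase about more than 5 of 27 patients not responding is a separate problem. The cut-off that matches the stated alpha and power is at least 8 responders of 27, a figure the protocol does not contain.

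In 4.4, add that the 90% power assumes 40% response among all 27 enrolled, with unevaluable patients counted as failures. Add that if 40% applies only to evaluable patients, power is 88%, 85%, 81% or 71% with 1, 2, 3 or 5 unevaluable.

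The change is wording in three sections, with no added patients or procedures. It discloses any loss of power without repairing it, since the sample size stays at 27. The price is a stated power and response rate that may look slightly less favourable.

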## 8.3 Statistical Analysis

All planned analyses will be performed for both the ITT and PP populations. A descriptive analysis of the primary and secondary endpoints will be conducted by determining relevant statistical parameters (including mean, median, standard deviation, minimum, maximum, absolute and relative frequencies, qualitative assessment of quality of life and side effects) and calculating the corresponding 95% confidence intervals. Furthermore, a descriptive analysis of the radiation treatment plans is planned. Endpoints collected at different time points (including side effects, quality of life, and PSA levels) will be described for each time point, and their temporal progression will be visualized graphically.

For endpoints that represent an interval until an event (progression-free survival, time to change of systemic therapy, overall survival), an evaluation is also performed using Kaplan-Meier curves and log-rank tests. In addition, a Cox regression analysis is conducted to investigate potential influencing factors on the respective analyzed endpoints.

If indicated by the patients, the reasons for premature discontinuation of therapy will be investigated. In addition, the reasons for withdrawal from the program documented by the center will be reviewed.

Study and loss-to-follow-up analyzed.

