#### 4.3.2 Radiation therapy of the prostate and metastases:

**Planned therapy:** The first radiation therapy is planned to be ultrahypofractionated prostate irradiation with 5 x 7.5 Gy on alternating days, analogous to the PACE-B trial [26], but without dose escalation to the CTV. Alternatively, if ultrahypofractionation is not possible (e.g., due to organ-risk exposure), moderate hypofractionated prostate irradiation with 20 x 3.0 Gy, analogous to the CHHiP trial [27], 20 x 2.75 Gy, or 6 x 6 Gy, analogous to STAMPEDE, can be performed.

Six months after radiation therapy to the prostate (calculated from the first day of radiation therapy), an ablative Radiation therapy for residual metabolically active metastases, preferably as stereotactic

Radiation therapy according to departmental standard (e.g., 3 x 10 Gy, 5 x 6 Gy) is planned. Alternatively, radiation therapy according to departmental standard can be performed moderately hypofractionated or normofractionated.

**Procedure:** In preparation for radiation therapy, an informational consultation is conducted, followed by a planning CT and planning MRI scan without contrast agent for treatment planning (two appointments on different days). After these preparatory examinations, radiation therapy is scheduled to begin within a maximum of 10 working days; in the meantime, treatment planning is carried out according to study guidelines.

Ultrahypofractionated prostate radiation therapy is performed under MRI guidance using an MRI/linear accelerator hybrid system, which allows for more precise soft tissue imaging than CT-guided radiation therapy. Furthermore, online adaptation of the treatment plan to the current anatomical conditions and monitoring of organ movement during radiation are possible. This allows for more precise determination of the position of organs at risk and adaptation to enable the selection of smaller safety margins (compensating for motion uncertainty as well as intra- and interfractional positioning uncertainty). This results in a lower dose to organs at risk and thus a reduction in long-term side effects. Imaging, plan adjustment, and radiation delivery take place over approximately 30 minutes.

45 minutes per radiation treatment. A total of 5 treatments of 7.25 Gy each are planned on alternating days, corresponding to a very short total treatment time of 2 weeks.

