- An increase in metabolically active lesions on PSMA imaging to a degree that prevents the implementation of local therapeutic measures.
- Acute toxicity CTCAE grade 4, showing no improvement.
- PSA doubling time < 6 months without imaging correlation.

If PSA levels rise during follow-up visits, the planned PSMA-PET/CT imaging for diagnostic purposes should be brought forward, and the study outpatient clinic should be consulted to determine whether newly occurring lesions should be treated with further local therapy.

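### The per-protocol time-to-event curves planned in section 8.3 are optimistic if time runs from enrollment or prostate radiotherapy, because per-protocol membership is decided only at about month 6; the ITT results are not affected

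*Protocol*

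**What the plan says.** Section 8.3 opens its analysis rules with "All planned analyses will be performed for both the ITT and PP populations". For the endpoints measured as an interval to an event (PFS, time to change of systemic therapy, OS) it adds that "an evaluation is also performed using Kaplan-Meier curves and log-rank tests", followed by Cox regression.

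Section 8.2 defines the two sets. ITT needs enrollment, at least one treatment and some baseline data. PP "comprises all patients in whom the planned therapy was fully completed according to the study protocol", and it is further limited to those "for whom all relevant data are complete and documented". Neither section ranks one set above the other for these endpoints.

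The planned therapy has two steps. Section 4.3.2 places the second, radiotherapy of the metastases that are still active, at this point: "Six months after radiation therapy to the prostate (calculated from the first day of radiation therapy". The visit schedule in section 7.1 also puts it at the 6-month visit.

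Section 5.5 lists reasons why the planned measures may have to be cancelled. They include "Disease progression necessitating the initiation of chemotherapy", a PSA increase with no locally treatable cause that calls for a change of systemic therapy, and "An increase in metabolically active lesions on PSMA imaging to a degree that prevents the implementation of local therapeutic measures".

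**The concern.** Whether a patient belongs to PP cannot be known at the start of treatment. It is settled at about month 6, and part of what settles it is the outcome under study: the cancellation reasons in section 5.5 are, or lead directly to, progression or a change of systemic therapy. A patient who fails early in one of these ways is removed from PP. A patient who stays has come through the first six months without a failure of that kind. If those six months count as follow-up time, the PP curve contains time during which such an event could not appear. This is the usual immortal-time problem.

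The protocol has no control arm (section 4.1), so absolute curves are the evidence on objective 2 in section 3.3, the influence of the therapy on oncological parameters. An optimistic PP curve would stand beside the ITT curve with equal rank, and part of any apparent gain would come from selection even if metastasis radiotherapy had no effect. The primary endpoint, the RECIP response rate, is not part of this point.

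**Working it through.** The protocol gives no figure for the time-to-event analyses, so there is none to reproduce. The check has two parts.

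**1. Which time origin is possible?** Section 8 states none. ITT includes a patient who received prostate radiotherapy alone (section 8.2). He has no date of metastasis radiotherapy, so an origin that serves both sets must lie earlier: enrollment or the start of prostate radiotherapy. The visit months in section 4.3.3 are also counted from enrollment. With such an origin, PP membership depends on what happens up to about month 6.

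**2. How large could the effect be?** Inputs:
- 2-year PFS of 40%, from the single-center series cited in sections 2.4 and 4.1. It comes from a different cohort, and section 2.4 counts it from metastasis-directed therapy, so it serves only as an illustration.
- Exponential curve: an assumption.
- Second step due at month 6 (section 4.3.2); 27 patients (section 4.4).
- f, the share of patients progressing before month 6 who leave PP: not given, so varied.

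Hazard: h = -ln(0.40)/24 = 0.0382 per month. PFS at month 6: S(6) = 0.40^(6/24) = 0.795. Progressing earlier: 1 - 0.795 = 0.205, or 5.5 of 27.

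Removed fraction: r = f × 0.205. Everyone removed has already progressed, so none would have counted as progression-free at 2 years. Hence PP 2-year PFS = 0.40/(1 - r), and PP median = -ln(0.5 × (1 - r))/h.

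| f | r | patients removed of 27 | PP 2-year PFS | PP median (months) |
|---|---|---|---|---|
| 0 (same as ITT) | 0 | 0 | 40.0% | 18.2 |
| 0.25 | 0.051 | 1.4 | 0.40/0.949 = 42.2% | 19.5 |
| 0.50 | 0.102 | 2.8 | 0.40/0.898 = 44.6% | 21.0 |
| 1.00 | 0.205 | 5.5 | 0.40/0.795 = 50.3% | 24.2 |

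Sensitivity, all with f = 1:
- True 2-year PFS of 30%: 0.30/0.740 = 40.5%, a gain of 10.5 points.
- True 2-year PFS of 70%: 0.70/0.915 = 76.5%, a gain of 6.5 points.
- 2-year PFS of 40% with the second step completed at month 7.5: S(7.5) = 0.751, and 0.40/0.751 = 53.3%.

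Check of the remedy: a simulation of the 40% curve gave 40.0% for all patients and 50.3% for those event-free at month 6 with time from the start. With the clock restarted at month 6, the same patients gave 40.0% at 24 months. The guaranteed time is gone. The return to exactly 40% is a property of the exponential curve; with another shape the landmark estimate would be a different, conditional quantity.

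**The case against.** Several counter-arguments carry weight.

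- **No time origin is stated.** Origin and landmark rules often sit in an SAP, and some follow-up in this protocol is counted from metastasis therapy (sections 4.3.3, 4.4 and 7.2). A reader might infer that the bias is built in whatever the analyst does; the text does not support that. What stands: the rule that every analysis is run in PP is in the protocol itself, and avoiding the bias requires PP to have its own origin, which section 8 does not provide.
- **ITT is reported too.** A reader might infer that all PFS and other time-to-event results are biased. They are not: ITT has no condition that depends on later events.
- **Progression is not the same as leaving PP.** Section 5.5 says only that cancellation may become necessary. Sections 4.2, 5.5 and 7.3 allow further local radiotherapy for isolated findings, so some patients who progress can stay in PP. Removal of all early progressors, which gives the 50% figure, is therefore an upper-end case for a given curve and timing. With a quarter removed the shift is about 2 points.
- **The 40% anchor is loose.** It is counted from metastasis-directed therapy in patients who received it, and the protocol plans no formal comparison with it. It cannot serve as a month-0 benchmark.
- **PP may not literally require metastasis radiotherapy.** A patient with no active lesion at month 6 has nothing to irradiate, and his PP status is not defined. It still cannot be known before about month 6.
- **The stakes are limited.** These are secondary endpoints in 27 patients with no decision rule attached. Sampling error is larger than the shift: 11 of 27 has an exact 95% interval of 22% to 61%. But the selection always pushes the curve upward, and an interval computed in PP does not show it.

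A reader might also infer biased log-rank and Cox comparisons. The protocol names neither groups nor covariates, so neither direction nor size can be stated. Nor can the data-completeness condition for PP be sized, because the relevant data are not listed.

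**Conclusion.** The concern holds in limited form. The protocol orders time-to-event analyses in a set whose membership depends partly on early failure. With time counted from enrollment or the start of prostate radiotherapy, the only kind of origin that also works for ITT patients who had prostate radiotherapy alone, the PP curves are optimistic. The ITT curves are sound in this respect.

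The size is unknown because the protocol gives no share of early progressors who would leave PP. The illustration gives a shift of about 2 to 10 points on a 2-year PFS of 40%. It rests on an exponential curve, a rate borrowed from another cohort with a different starting point, and removal of 25% to 100% of early progressors. It shows the order of magnitude and is not an estimate for this trial. No size is given for OS or time to change of systemic therapy. The point still deserves a change, because it concerns a stated rule, the trial has no control arm, and the correction is simple.

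**What to change.** In section 8.3, make ITT the main population for the time-to-event endpoints, with time counted from the start of prostate radiotherapy. Allow a PP time-to-event analysis only as a landmark analysis: the clock starts at completion of metastasis radiotherapy, only patients free of the event in question at that point enter, and the result is labelled as conditional on reaching it. The text should also say how a patient with no active lesion left at month 6 is classed and from which date he is counted.

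This takes a few sentences and no extra data, since radiotherapy is already documented in the eCRF (section 6.3.4). The downside is that the PP curves start later, include fewer patients and look less favourable. The landmark removes the guaranteed time but not the selection, so the PP result remains a statement about patients who got that far.
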